5.11 Treatment-Emergent Adverse Event (TEAE)

A TEAE is defined as an AE with a start date or worsening during the On-Treatment Period for TEAEs (see Section 5.3 for definition of the On-Treatment Period).

If the start date for an AE is missing and the end date is either missing or on or after the date of first dose of study medication, then the AE will be assumed to be treatment-emergent. However, if the start date for an AE is missing and the end date is recorded and is before the first dose of study medication, then the AE will be assumed to be non-treatment emergent.

5.12 Quality of Life Enjoyment and Satisfaction Questionnaire Short Form (Q-LES-Q-SF)

The total score of the Q-LES-Q-SF (see Appendix 4 of the Protocol) will be derived by summing the first 14 items to obtain the raw total score. The raw total score is then transformed into a percentage maximum using the following formula:

$$Percentage Maximum = \frac{(raw \ total \ score - \ 14)}{56}$$

In the case of questions with missing results, if 10 or more questions are answered, then the percentage maximum is derived as follows:

 $Percentage Maximum = \frac{(raw \ total \ score \ for \ the \ questions \ answer - \ number \ of \ questions \ answer)}{(the \ number \ of \ questions \ answered \ \times \ 4)}$

If fewer than 10 questions are answered, then the percentage maximum will be considered to be missing.

The change from Baseline at the end of treatment will be calculated for each subject.

5.13 Menstrual Distress Questionnaire

The Menstrual Distress Questionnaire (see Appendix 5 of the Protocol) will be scored according to the manual (Moos, 1968). The following scales will be derived by summing the items that fall within that specified category: pain, water retention, autonomic reactions, negative affect, impaired concentration, behavior change, arousal and control. Each of these are derived at each visit for the menstrual (most recent flow in CRF), premenstrual (4 days before in the CRF) and intermenstrual (remainder of the cycle in the CRF) phases by summing the items that fall under the specified scale. The scoring key is presented in **Table 3** below. If the subject does not answer one item on any of the scale, then the scale is calculated by deriving the mean score for the answered items and adding that number to the sum of the answered items within that scale. If 2 or more items within a scale are not answered, then the scale is missing. The change from Baseline at the end of treatment will be calculated for each subject.

Scale	Items
Pain	1, 2, 3, 4, 5, 6
Water Retention	7, 8, 9, 10
Autonomic Reactions	11, 12, 13, 14
Negative Affect	15, 16, 17, 18, 19, 20, 21, 22
Impaired Concentration	23, 24, 25, 26, 27, 28, 29, 30
Behaviour Change	31, 32, 33, 34, 35
Arousal	36, 37, 38, 39, 40
Control	41, 42, 43, 44, 45, 46

Table 3: Menstrual Distress Questionnaire Scoring Key

5.15 Methods for Handling Missing Data

5.15.1 Missing Data Related to the Pearl Index and Pill Intake

In the derivation of the Pearl Index, if the subject did not respond to the question on other contraceptive methods in the subject diary, it will be assumed that another contraceptive method was used. The cycle will be classed as a not at-risk cycle and excluded from the denominator of the Pearl Index. If the subject did not respond to the question on sexual intercourse in the subject diary, it will be assumed that she did not

have sexual intercourse and that cycle will be classed as a not at-risk cycle and excluded from the denominator of the Pearl Index as appropriate.

For compliance, if the number of active (pink) and inactive (white) pills is blank in the diary, then it will be assumed that no pills were taken on that day.

If there is a partial start date for a cycle, then the start date will be imputed as the day after the date of Day 28 of the previous cycle, providing the imputed date is consistent with the non-missing part of the date reported and that the duration of the cycle is consequently consistent with the expected 28 days. For rules around missing or partial start dates for Cycle 1, see Section 5.15.5.

5.15.3 Missing or Partial Dates for Medications

In the determination of whether a medication is taken during the On-Treatment Period, the following rules for missing and partial dates will be applied:

- If the end date is before the first dose of study medication, then the medication is a prior medication, regardless of whether or not the start date is missing or partially missing
- If the end date is on or after the date of first dose of study medication, then the following rules will be applied for missing or partially missing start dates:
 - If the start date is completely missing, then the medication will be assumed to be concomitant.
 - If only the year of the start date is recorded and the year is either before or the same year as the end of the safety On-Treatment Period, then the medication will be assumed to be concomitant.
 - If only the year of the start date is recorded and the year is after the year of the end of the safety On-Treatment Period, it will be considered to be a post-study treatment medication.
 - If only the year and the month of the start date is recorded and the month specified is either before or the same month as the end of the safety On-Treatment Period, then the medication will be assumed to be concomitant
 - If only the year and the month of the start date is recorded and the month specified is after the month of the end of the safety On-Treatment Period, it will be considered to be a poststudy treatment medication.

Rules for dealing with missing start and stop dates for study medication for the classification of medications are in Section 5.15.5.

5.15.4 Missing or Partial Dates for AEs

If the start date for an AE is missing and the end date is either missing or on or after the date of first dose of study medication, then the AE will be assumed to be treatment-emergent. However, if the start date for an AE is missing and the end date is recorded and is before the first dose of study medication, then the AE will be assumed to be non-treatment emergent.

Rules for dealing with missing start and stop dates for study medication for the classification of AEs are in Section 5.15.5.

5.15.5 Missing or Partial Treatment Start and Stop Dates

5.15.5.1 Missing Treatment Start and Stop Dates

If the subject has no diary data but has a pregnancy as per Principal Investigator's assessment in the pregnancy narrative that is classified as on-treatment or post treatment, then the subject will be classed as treated. The treatment start date and treatment stop date would be unknown in this situation.

In the case of post-treatment pregnancies, the cycle for censoring for the cumulative event rates for pregnancies cannot be determined and this will be missing. The subject will also consequently have no evaluable cycles for the Pearl Index. In the case of on-treatment pregnancies, the cycle of conception from the narrative will be used in the derivation of the cumulative event rates for pregnancies and in the derivation of the Pearl Index no other cycles would be included in the denominator for that subject.

When classifying concomitant, pre- and post medication and treatment emergent AEs and defining the Baseline assessments, the treatment start date will be assumed to be the first date in which the investigational product was dispensed and the treatment end date will be assumed to be the discontinuation or completion date for that subject. However, the start and stop dates for study medication will remain missing and the compliance and exposure will not be calculated. Similarly, the cycle of discontinuation of study medication cannot be determined and therefore this would remain missing for such subjects. The subject will have no evaluable cycles for the bleeding analysis.

5.15.5.2 Partial Treatment Start Dates

If the subject has a partial start date Cycle 1, and consequently a partial start date for study medication, then the partial start date will be presented in the listing. If the date of last dose cannot be derived as a result of the partial start date, then this will be blank in the listings as the end date is unknown.

In the case of an on-treatment pregnancy, the cycle of conception will be estimated from the available data. If the subject does not have an on-treatment pregnancy, then for the cumulative event rates for pregnancy, the subject will be censored in the cycle where the last pill intake was reported per the diary data. Cycle 1 will be included in the denominator for the Pearl Index following the rules in Section 5.1.1 and will be included in the bleeding analysis following the rules in Section 5.1.2.

In this case, when classifying concomitant, pre- and post medication and treatment emergent AEs and defining the Baseline assessments, the treatment start date will be assumed to be the first date in which the investigational product was dispensed. If the treatment end date cannot be determined as a result of the partial start date, then the date of last dose will be derived for the day in the diary where the last pill is reported and by assuming that the start date is the latest possible day. For example, if the partial start date is January 2017 and the last day with a pill reported is Day 4 of Cycle 1, then the assumed start date would be 31 January 2017 and therefore Day 4 of Cycle 1 would be 3 February 2017 and this would be used as the date of last dose. The diary data for pill intake will be used to derive compliance and exposure per the rules in the SAP.

6.0 Analysis Sets

6.1 Screened Population

The Screened Population includes all subjects who signed an informed consent (IC) form.

The Screened Population will be used for disposition data and data will be displayed for subjects aged 16 to 35 years and for all subjects in separate columns.

6.2 Enrolled Population

The Enrolled Population includes all enrolled subjects (i.e. subjects who had a non-missing enrollment date on the enrollment page of the CRF).

The Enrolled Population will be used for summaries of enrollment per country.

6.3 Safety Population

The Safety Population includes all enrolled subjects who receive at least one dose of study medication.

If a subject returns all study medication that was dispensed, then the subject will not be included in the Safety Population. If there is at least one pill that was dispensed but was not returned, but the subject diary has no pills recorded as taken, then it will be assumed that the subject has not taken any study medication and will not be included in the Safety Population. However, if the subject has no pills taken according to the diary but the subject has a pregnancy that is classified as per Principal Investigator's assessment in the pregnancy narrative as either an on-treatment or post treatment pregnancy, then the subject will be included in the Safety Population. In the case of missing diary data, it will be assumed that no pills were taken for the corresponding days with missing data. If there was at least one pill that was dispensed but was not returned and the subject has taken at least one pill according the subject diary, then that subject will be included in the Safety Population.

The Safety Population will be used for compliance and exposure data with data displayed for subjects aged 16 to 35 years and for all subjects in separate columns. The Safety Population will also be used for safety presented for all subjects.

Follow-up evaluations will be presented for subjects in the Safety Population who discontinued study medication with pregnancy wish as the reason for discontinuation.

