12.2 Analysis Populations and Datasets

Statistical analysis and data tabulation will be performed using the following analysis populations unless specified otherwise:

- Screened population includes all subjects who signed an IC form.
- Enrolled population includes all enrolled subjects.
- Safety population includes all enrolled subjects who receive at least one dose of test article.
- Intention-to-Treat (ITT) population includes all enrolled subjects who receive at least one dose of test article. The ITT population is the same as the Safety population for this study.
- Per-protocol (PP) population includes all subjects in the ITT population who complete the study and do not have any important protocol deviations that impact the statistical analysis. The PP population may differ for the different endpoints.
- PK population includes all subjects enrolled in the PK Substudy who provide concentration data for at least one sample.

FSTMTRA

All the analyses will be conducted with SAS using procedures appropriate for the particular analysis.

The descriptive statistics for all the continuous variables presented will be mean, median, 25th percentile, 75th percentile, standard deviation (SD), standard error of mean (SEM), minimum, maximum, and number of subjects.

Categorical variables will be summarized using counts and percentages.

Baseline will be defined as the most recent assessment prior to first dose of study medication.

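### A woman with unreturned tablets and no diary intake counts as untreated even when other records show she took product; only a pregnancy overrides this

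*SAP*

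**What the plan says.** Protocol 12.2 sets a simple criterion: "Safety population includes all enrolled subjects who receive at least one dose of test article". SAP 6.3 opens the same way: "The Safety Population includes all enrolled subjects who receive at least one dose of study medication". It then adds rules for deciding whether a dose was received.

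- A woman who returned everything dispensed is out.
- The disputed case is: "If there is at least one pill that was dispensed but was not returned, but the subject diary has no pills recorded as taken", and the consequence is "then it will be assumed that the subject has not taken any study medication and will not be included in the Safety Population".
- A blank or lost diary meets that condition: "In the case of missing diary data, it will be assumed that no pills were taken for the corresponding days with missing data".
- The one exception begins "if the subject has no pills taken according to the diary but the subject has a pregnancy" and requires that the investigator's narrative classify it "as either an on-treatment or post treatment pregnancy, then the subject will be included in the Safety Population".

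SAP 9.1 uses the same rule to decide who is counted as treated. SAP 5.15.5.1 covers women with no diary who enter through the pregnancy exception. For classifying events, "the treatment start date will be assumed to be the first date in which the investigational product was dispensed", and the end date is the discontinuation or completion date.

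TEAE incidence is tabulated in the Safety Population (SAP 9.6.1), and the annual rate divides events by total exposure in that population (SAP 5.8, 9.6.1). The AE and SAE listings use the Screened Population (SAP 9.6.1, 9.6.2). The ITT Population is identical to the Safety Population (SAP 6.4).

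**The concern.** The rule lets one kind of evidence outweigh an empty diary and ignores every other kind. An investigator's narrative about a pregnancy can establish that a woman was treated. An investigator's judgement that a serious event was related to study drug cannot. Membership of the safety set thus depends partly on which outcome occurred, and a woman with good documentary evidence of intake can be classed as never treated.

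At stake are the TEAE and SAE tables. If such a woman has an event, it appears in neither the numerator nor the denominator of the incidence tables, and it is not in the annual rate.

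**Working it through.** The plan states no figure that depends on this rule, so the main check sets the sections side by side.

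**1. Can the situation arise?** Product and diary are both handed out at Visit 2, and both are first collected at Visit 3 in Cycle 2 (Protocol 9.4.1.2, 9.5.2, 9.5.3.1, 9.6.1). A woman who starts, stops during Cycle 1 and does not come back leaves neither blisters nor diary, which is exactly the excluding condition.

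**2. What other evidence of intake could exist?**

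- *Relatedness.* In Protocol 9.6.3.1 the possible, probable and highly probable categories each require a plausible or reasonable time relation to drug intake. An event rated related therefore implies a judgement that drug was taken.
- *Site-recorded dosing.* In the PK substudy, staff enter the time of the last dose in the eCRF (Protocol 9.6.4.2).
- *Plasma concentration.* A woman with concentration data for one sample is in the PK Population (SAP 6.6). With a measurable concentration, an unreturned tablet and a blank diary she would be in that set and outside the Safety Population. This can affect only women among the roughly 500 in the substudy who reach Visit 3.
- *The woman's account.* Protocol 9.4.3 has the investigator discuss diary-tablet discrepancies with her and document them in the source. SAP 6.3 makes no use of that record.

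**3. Does another section rescue her?** Safety Population membership is not among the data review topics in SAP 8.3. The date conventions in SAP 5.15.5.1 are written for women admitted by the pregnancy exception. Without a first-dose date her events cannot be classed as treatment-emergent under SAP 5.11.

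**4. How do the documents treat similar uncertainty elsewhere?** Protocol 9.6.2.2, on pregnancy follow-up, takes return of all product as proof of never starting; an empty diary is not mentioned. SAP 5.11 and 5.15.4 class an event with no start date as treatment-emergent unless its end date precedes the first dose. SAP 6.3 resolves uncertain exposure the other way.

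**5. Size, as a range.** The number of such women who took product, m, is not in the documents, so m is assumed. The planned 2000 women are taken as tabulated, and 50% with a TEAE is also assumed. Adding back m women of whom none to all had a TEAE gives 1000/(2000 + m) to (1000 + m)/(2000 + m). For an event with an assumed risk of 1 in 1000, the chance that at least one falls among the m women is 1 − 0.999^m.

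| m | TEAE percentage after adding back | Chance that a 1-in-1000 event is among them |
|---|---|---|
| 5 | 49.9 to 50.1 | 0.5% |
| 20 | 49.5 to 50.5 | 2.0% |
| 50 | 48.8 to 51.2 | 4.9% |
| 100 | 47.6 to 52.4 | 9.5% |

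**6. What one omitted event does to a rate.** Protocol 12.1 assumes 45% dropout with 4 cycles on average among dropouts. Applied here to all 2000 women, that is 0.55 × 13 + 0.45 × 4 = 8.95 cycles each. Then 2000 × 8.95 × 28 / 365.25 ≈ 1,372 woman-years, and 1/1,372 ≈ 7.3 per 10,000 woman-years. This shows the effect of one omission; it does not predict that one will occur.

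**7. Pearl Index.** For a woman with no diary, the unanswered contraception and intercourse questions make her cycles not at risk (SAP 5.15.1), so adding her leaves the primary Pearl Index unchanged.

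**The case against.** The strongest reply is that intake in this group is unknown. The protocol itself produces non-starters after dispensing. Product is handed out at Visit 2, but a woman must not start if her cycle length is out of range or her home pregnancy test is positive (Protocol 9.4.4.1, 9.5.2), and the Early Termination Visit provides for product never started (9.5.4). A non-starter lost to follow-up also leaves tablets unreturned. This stands: the documents do not show that the excluded women were exposed.

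A reader might infer that the rule biases TEAE incidence downward. The documents do not support that. Excluded women leave both numerator and denominator, and the table above moves in either direction. A downward bias needs a higher event rate in this group, which no section establishes.

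A reader might also infer that any adverse event or discontinuation is as good evidence of intake as a pregnancy. It is not. Events are collected from consent, before any dose (Protocol 9.6.3.1), and some women who never start must be withdrawn. The pregnancy exception rests on an investigator's classification relative to treatment; an event assessed as related is comparable, an unrelated one is not. Admitting women for any event would select cases and could label pre-dose events as treatment-emergent.

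Nor does SAP 6.3 simply contradict the protocol. It keeps the one-dose criterion and adds a way of deciding whether it was met.

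Finally, the events are not hidden. SAEs are reported within 24 hours (Protocol 9.6.3.1), and all AEs, all SAEs, related SAEs and AEs leading to discontinuation are listed in the Screened Population. That limits the harm but does not put the events into the incidence tables or rates. It also means that a related SAE could be listed for a woman whom the tables class as untreated.

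**Conclusion.** The point holds in a limited form. SAP 6.3 and 9.1 let an empty or missing diary outweigh all documented evidence of intake except an on- or post-treatment pregnancy. A woman who demonstrably took product can therefore be left out of the TEAE incidence tables and annual rates while her events remain in the listings.

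The number of women and the direction for common events are unknown, and the effect on common TEAE percentages is probably small: within half a percentage point for 20 women, under the assumptions shown. The case for change rests on a rare or early serious event, where one omission would shift a rate by about 7 per 10,000 woman-years at the planned exposure. It does not rest on a claim that the excluded women were exposed or that the tables are biased in a known direction.

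**What to change.** In SAP 6.3 and 9.1, replace the pregnancy-only exception with any documented evidence of intake. Name an on- or post-treatment pregnancy, an AE or SAE assessed as related to study drug, a dosing time recorded by the site, a measurable E4 or DRSP concentration, and the woman's own account documented under Protocol 9.4.3. Extend the SAP 5.15.5.1 date conventions to these women.

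Add a sensitivity TEAE/SAE table that includes every woman with unreturned tablets unless the site documents that none was taken. Its membership does not depend on an outcome, so it also checks any selection introduced by admitting women because of a related event.

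The cost is SAP wording and one table, with these side effects:

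- The sensitivity set may contain some never-takers.
- Taking the dispensing date as the start may class some events before the first tablet as treatment-emergent.
- A few women without diary data enter the Safety and ITT sets with compliance, exposure and discontinuation cycle missing. The SAP should say how they are handled in the discontinuation life table. It should also say that in the annual rate their events would count without matching exposure.

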6.4 Intention-to-Treat (ITT) Population

The ITT Population includes all enrolled subjects who receive at least one dose of study medication. The ITT Population is the same as the Safety Population for this study.

The ITT Population will be used for baseline and contraceptive efficacy data with data displayed for subjects aged 16 to 35 years and for all subjects in separate columns. The ITT Population will also be used for protocol deviations, bleeding and quality of life data with data presented for all subjects.

6.5 Per-Protocol (PP) Population

The bleeding data cycle analysis will be presented in the PP Population. For the bleeding analysis, the PP Population will exclude cycles based on the rules in Section 5.1.2. Subjects in the ITT Population with at least one evaluable cycle for the bleeding analysis will be included in the PP Population and only their evaluable cycles will be included in the PP analysis for bleeding data. Subjects will be excluded from the PP Population entirely if they have no evaluable cycles for the bleeding analysis.

